Methods: Data will be collected at four measuring points: at baseline (during hospital admission for the ICH or at the outpatients clinic within one month of presentation with an acute ICH), after three months, after six months and after 12 months. Premorbid cognitive functioning will be assessed with the Informant Questionnaire on Cognitive Decline in the Elderly (IQCODE) to select participants without pre-existing cognitive impairment.

At baseline, the premorbid functional status will be assessed with the modified Rankin Scale (mRS) and Barthell index. A 3Tesla MRI will be performed to assess the most likely underlying cause of the ICH (patients with either CAA or HA-related ICH will be included). Stroke severity will be assessed with the National Institutes of Health Stroke Scale (NIHSS) and a neurologic exam will be performed. Participants will undergo an extensive interview on life-style, vascular risk factors and medication, and

will undergo a blood withdrawal. Neuropsychological testing will be performed and questionnaires will be used for screening for depression, anxiety and psychopathology. In addition, participants will be asked to undergo a lumbar puncture to collect cerebrospinal fluid (CSF).

After three months, neurological examination, and neuropsychological testing will be repeated.

After six and 12 months, the neurological examination, the 3 Tesla MRI and neuropsychological testing will be repeated. Additionally, participants will be asked for a lumbar puncture at these two time points.

Main study parameters/endpoints: The main parameters are cognitive decline (according to the neuropsychological assessment) at 12 months. Secondary outcomes are burden of SVD markers on MRI and CSF markers at baseline, at six months and 12 months.

Nature and extent of the burden and risk associated with participation, benefit and group relatedness: The risks of MRI are minimal (risk of everyday life), because there are no consequences to the health of the participant. Contra-indications will be carefully investigated per subject, burden will be kept at a minimum by using short protocols. There is no direct benefit for the patients except for more insight into the underlying pathophysiology of the hemorrhages related to their disease.

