The incidence of new-onset dementia after stroke has been addressed in a cohort of 218 ICH patients. In these ICH survivors without dementia at baseline, new-onset dementia occurred with an incidence of 14.2% at 1 year and 28.3% at 4 years of follow up. Interestingly, this incidence was twice as high in patients with lobar ICH (23.4% at one year follow-up) than for patients with non-lobar ICH (9.2% at one year follow-up). This finding is in line with previous studies linking CAA to cognitive impairment.⁶

MRI markers and cognitive impairment

Underlying SVD-related pathology can be identified using MRI. Even though MRI does not show the entire spectrum of the underlying SVD pathology, it has improved our understanding of SVD pathology extensively in the recent years.⁷ MRI markers associated with CAA often are different or have a different distribution compared with MRI markers associated with HA.⁸ Deep cerebral microbleeds (MB's), white matter hyperintensity (WMH), and MRI visible enlarged perivascular spaces (ePVS) located in the area of the basal ganglia are associated with HA.⁹ Markers associated with CAA include lobar MB's, WMH, ePVS in the subcortical white matter, cortical subarachnoid hemorrhage (cSAH), intragyral hemorrhages, microinfarcts, cortical thinning, and cortical superficial siderosis (cSS).⁴

Severe WMH, lacunar infarcts, microinfarcts, have been associated with vascular cognitive impairment.¹⁰ The association between cognitive impairment and MB's has also been well established,¹¹ and recent studies have shown that cSS plays an important role in predicting progression of CAA.^{12, 13} Additionally, altered white matter integrity measured with diffusion tensor imaging (DTI) has been found in patients with mild cognitive impairment¹⁴ and CAA¹⁵ and might be a marker of cognitive decline in post-ICH patients.

As both HA and CAA are likely to progress over time, and therefore continue to damage the brain, it can be assumed that these two forms of SVD cause further cognitive deterioration after ICH and that this can be demonstrated by progression of the burden of MRI markers.

Biomarkers in cerebrospinal fluid

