5.2 Inclusion criteria

ICH patients:

1. Age ≥ 55 y
2. Ability and willingness to provide written informed consent.
3. Supratentorial ICH with CAA^a or HA^b as the most likely cause.

^a CAA-related ICH is defined as an ICH that meets the criteria for definite or probable CAA according to the Modified Boston Criteria (appendix A)

^b HA-related ICH is defined as ICH located in the basal ganglia, thalamus, or the deep white matter and the presence of hypertension defined as: on treatment for hypertension, or known with high blood pressure (two measurements SBP >140 or DBP >90 mmHg) but not treated for hypertension.

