5.4 Sample size calculations

For this pilot study, we require 32 participants (16 CAA-related ICH and 16 HT-related ICH). This sample size is considered to be sufficient to study the feasibility of the study procedures. Furthermore, the results of a pilot study with this sample size should provide sufficient data that are needed to determine a sample size of a future, larger cohort study.

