8. STATISTICAL ANALYSIS

Descriptive statistics will be performed. New onset cognitive impairment and dementia will be determined (according to the MMSE scale) and compared between CAA-related and HA-related ICH. Prevalence of different biomarkers in CSF and MRI and their evolution over time will be assessed. Linear regression analysis will be used to examine associations of MRI and CSF markers primarily with the MMSE and secondarily with the other cognitive scores. Some MRI markers, such as MB's count will be transferred logarithmically. Based on our power calculation (see references paragraph 5.4) we expect that the number of participants will be sufficient for analyses of difference in cognitive decline between CAA-related ICH and HA-related ICH. This pilot study is, however, not powered to detect significant associations between cognitive decline, MRI markers and CSF markers. The

evolution of MRI and CSF markers will, however, give enough insight to power a larger trial to investigate the underlying mechanisms of cognitive decline after ICH. In addition, we will assess whether levels of MRI and CSF markers change between 6 and 12 months after the ICH to decide which timepoint is most relevant for a larger study as in the subsequent study we aim to have one follow-up time point for a MRI and lumbar puncture.

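### Section 8 rests the CAA-versus-HA comparison on a power calculation in Section 5.4 that Section 5.4 does not contain

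*Protocol*

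**What the plan says.** Section 8 (Statistical analysis) makes two statements about power, one after the other. For the group comparison it refers to a power calculation in Section 5.4 and says: "we expect that the number of participants will be sufficient for analyses of difference in cognitive decline between CAA-related ICH and HA-related ICH". For the markers it says: "This pilot study is, however, not powered to detect significant associations between cognitive decline, MRI markers and CSF markers".

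Section 5.4 (Sample size calculations), to which Section 8 refers, sets 32 participants, 16 per group, and gives two reasons. The first is feasibility: "This sample size is considered to be sufficient to study the feasibility of the study procedures". The second is that the pilot "should provide sufficient data that are needed to determine a sample size of a future, larger cohort study". It gives nothing else.

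The comparison matters because of the Summary: "The main parameters are cognitive decline (according to the neuropsychological assessment) at 12 months". Objective 1 in Section 3 adds the proportion with new-onset dementia in each group, and Section 8 plans to compare new-onset impairment and dementia between the groups.

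**The concern.** Section 8 cites support that is not there. Power follows from an outcome, an effect, a variance or event rate, an alpha and a sample size. Of these, Section 5.4 gives only the sample size.

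The claim cannot be read as meaning merely that there are enough patients to run the analysis. It is tied to a power calculation, and the next sentence contrasts it with the marker associations, for which power is expressly denied. A reader will conclude that the CAA-versus-HA comparison is powered.

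So the protocol warns about low power for the secondary marker analyses and reassures on the main parameter. It does not say that a non-significant result will be read as no difference, but nothing in it guards against that reading. The results are meant to design a larger cohort, so such a misreading could carry over into that design.

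**Working it through.** **Plan's own figure.** The 16 per group cannot be reproduced, because Section 5.4 states no inputs. The calculations below only illustrate what 16 per group can do.

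**Inputs**
- n = 16 per group: Section 5.4.
- One-year new-onset dementia, 23.4% (lobar) and 9.2% (non-lobar): Section 2. The protocol does not link these rates to the sample size.
- Two-sided 5% level and 80% power: assumed, as the protocol states neither.
- Rates of 50% versus 25% for a broader impairment outcome: assumed.
- Baseline correlation r of 0.5 to 0.8 for a continuous score: assumed.

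The dementia rates are a proxy. Lobar is not the same as CAA, which Section 5.2 defines as definite or probable by the Modified Boston Criteria. Non-lobar is not the same as HA: "HA-related ICH is defined as ICH located in the basal ganglia, thalamus, or the deep white matter and the presence of hypertension". Dementia is also not the main parameter, although it is Objective 1.

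**1. Dementia proxy, 23.4% versus 9.2%**

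Expected cases: 16 × 0.234 = 3.7 and 16 × 0.092 = 1.5.

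Power, by exact enumeration of two Binomial(16) outcomes: 8.9% (Fisher) and 18.3% (uncorrected chi-square).

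Sample size for 80% power, with p̄ = (0.234 + 0.092)/2 = 0.163:

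n = [1.960·√(2p̄(1−p̄)) + 0.842·√(p₁(1−p₁) + p₂(1−p₂))]² / (p₁−p₂)²

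= [1.960 × 0.5224 + 0.842 × 0.5126]² / 0.142² = 2.118 / 0.02016 = 105.03, so 106 per group.

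95% CI around the assumed difference: 0.142 ± 1.960·√(0.2628/16) = 0.142 ± 0.251, or about −11 to +39 percentage points.

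A one-sided 5% level does not rescue the claim. Fisher power is then 12.4%, and 80% power needs 83 per group. Against 9.2%, 16 per group has 80% two-sided power only if the other group's rate is about 53.5% (normal approximation) or about 60% (Fisher).

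**2. Assumed broader outcome, 50% versus 25%**

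Power: 18.4% (Fisher) and 32.0% (chi-square).

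The same formula gives 57.67, so 58 per group for 80% power.

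95% CI: 0.25 ± 1.960·√(0.4375/16) = 0.25 ± 0.324, or about −7 to +57 points.

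**3. Continuous score, smallest difference detectable with 80% power**

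| Analysis | Difference needed |
|---|---|
| Two-sample t-test, 30 df | 1.024 SD |
| Baseline-adjusted, r = 0.5 | 0.888 SD |
| Baseline-adjusted, r = 0.7 | 0.732 SD |
| Baseline-adjusted, r = 0.8 | 0.615 SD |

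The adjusted rows use 29 df and a residual SD factor of √(1−r²). The protocol gives no expected difference, SD or correlation to set against these values.

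**The case against.** The best case for the protocol has four parts.

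- **It is a pilot.** The protocol says so repeatedly, Section 8 opens with descriptive statistics, and no alpha or decision rule is set for the group comparison. This is true, and it is why 16 per group is not criticised here. It does not excuse citing a power calculation that is absent. It also makes the claim harder to understand, since Section 2 says the pilot's results will be used to power a larger study that covers differences between CAA and non-CAA pathology.
- **A calculation may exist but have been left out.** The normal-approximation formula for a 1.0 SD difference, 80% power and two-sided 5% gives 2 × (1.960 + 0.842)² = 15.7, so 16 per group. That match cannot be dismissed. But the protocol states no such assumption, and the outcome it would refer to is unknown.
- **The figures do not prove insufficiency for every endpoint.** This stands. For a continuous score they show what difference would be needed, not that it is implausible. They show the claim to be unsubstantiated. Only under the dementia proxy and the assumed 50% versus 25% rates is power shown to be low.
- **Sample size detail may sit in a statistical analysis plan.** This fails, because Section 8 points to Section 5.4 of the same protocol, and nothing there is marked as removed.

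The error is an internal contradiction rather than a slip in arithmetic, and correcting it changes nothing in the conduct of the study. Even so, it is a wrong statement about the main parameter.

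**Conclusion.** The concern holds. Section 8 attributes to Section 5.4 a power calculation that Section 5.4 does not contain, and on that basis calls the sample sufficient for the comparison on the main parameter. This follows from the text alone and needs no assumption.

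The size of the gap does rest on assumptions: two-sided 5%, the lobar/non-lobar dementia rates as a proxy, and the assumed impairment rates and correlations. Under them, power for a binary outcome lies between 8.9% and 32.0%, and 80% power needs 58 to 106 per group. A continuous score would need a difference of roughly 0.6 to 1.0 SD. Sixteen per group may be reasonable for a pilot, but the protocol gives no ground for calling it powered for this comparison.

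**What to change.** In Section 8, delete the sentence that claims sufficiency, with its reference to Section 5.4, and replace it with:

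> *This pilot study is not powered to compare cognitive decline between CAA-related and HA-related ICH. Differences will be reported as estimates with 95% confidence intervals, and a non-significant result will not be interpreted as no difference.*

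The following sentence on marker associations should then lose its contrasting 'however', since both statements point the same way. The feasibility reasoning in Section 5.4 can stay as it is.

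If a power figure is quoted, label it as new-onset dementia in lobar versus non-lobar ICH used as a proxy, and state the alpha and the test. If a calculation for this comparison does exist, the alternative is to set it out in Section 5.4 with its outcome, effect, variance or rates, alpha and power, so that the cross-reference becomes true.

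The cost is wording only: no extra patients and no change to procedures or data. The one drawback is that the protocol will make a less favourable statement about power.

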9. ETHICAL CONSIDERATIONS

9.1 Regulation statement

The study will be conducted according to the principles of the "Declaration of Helsinki" (as amended in Fortaleza, Brazil, October 2013) and in accordance with the Guideline for Good Clinical Practice (CPMP/ICH/135/95 - 17th July 1996).

9.2 Recruitment and consent

The protocol of this study will be submitted to the Medical Ethics Committee of the Leiden University Medical Center and the study will not commence before formal approval has been granted.

Participants will be selected from our LUMC ICH population. This population consists of patients referred to our emergency department for ICH and are admitted to our clinic. Patients will be contacted by one of the neurologists, neurologic residents or research physicians. In addition, neurologists from other hospitals can send their patients who want to participate in our study if they are < 1 month after ICH onset. The purpose of the study will be explained and the eligible participants will receive a letter with information about the study. The purpose and method of the study will be described in the information letter (see attachment 'proefpersoneninformatie'). Participants who are not able to give informed consent will not be included in the study. All participants are free to discontinue the study at any time. Participation in this study will have no negative financial consequences for the patient, travel expenses will be compensated for.

Written informed consent will be obtained for the (repeated) 3T MRI, venous puncture and lumbar puncture. Subjects will be asked for a written informed consent for future projects with blood and CSF stored for biobanking purposes.

Investigations at the different time points can take place on a single day at each time point, depending on the preference of the patient.

9.3 Benefits and risks assessment, group relatedness

To learn more about the pathophysiology, progression and prognosis of cognitive decline after ICH, we need to investigate ICH patients over a long period of time. By investigating MRI markers, CSF markers and cognitive functioning we will obtain more insight on individuals at risk. Moreover, this study hopefully eventually leads to new targets for therapy and will give insight in the sample size needed for a larger study to investigate mechanisms behind cognitive decline after ICH. Patients will

be informed extensively about the potential risks of the study procedures, after which written informed consent will be obtained.

The potential risks of this study are limited. The risks of gadolinium enhanced 3Tesla MRI are minimal. Gadolinium enhanced 3T MRI is performed in patients with ICH in routine clinical practice as part of the workup to find an underlying cause such as a tumor or a macrovascular cause according to the guidelines of the American Heart Association (2015) and the European Stroke Organisation (2019). Deposits of gadolinium can remain in the brains of some patients who have undergone 4 or more MRI scans with gadolinium for a prolonged time after the last administration. Deposits of gadolinium have also been reported in skin and bone. The European Medicines Agency has concluded that there is no evidence that gadolinium deposition in the brain has caused any harm to patients. A nephrogenic systemic fibrosis (NSF) has also been reported after gadolinium-based contrast agent administration. The most important risk factor for NSF is a severely reduced kidney function ($eGFR < 30 \text{ ml/min/1.73m}^2$). The type of gadolinium-based contrast agent is also determinant for the risk of NSF. Allergic reactions to gadolinium-based contrast agents have also been reported. Other potential risks include movement of ferromagnetic objects in the body. Some participants may feel claustrophobic in the restricted space of the MR scanner.

The potential risks related to MRI will be minimized in the following manner:

- Claustrophobia

Claustrophobia from the MRI scan will be reduced by explaining the nature of the scanner in detail before enrolment. At all times, the subjects will be able to communicate with the researcher, so if claustrophobia becomes a problem the subject can request to be removed from the scanner.

- Movement of ferromagnetic objects in the body

A list of questions concerning risk factors of MRI must be filled in by the subject. Based on the answers the subject is or is not allowed to go into the scanner.

- Gadolinium will be administered once, the administered dose of gadolinium will be kept as low as possible, and a macrocyclic gadolinium-based contrast agent (Gadoteraat (Dotarem 0,5 mmol/ml, Guerbet) will be used to maximize safety. After administering gadolinium participants will be under observation for at least 30 minutes to check on signs of an allergic reaction. Participants will be advised to avoid repeated gadolinium administering in the next 24hours and creatinine clearance will be checked for reduces kidney function.

Blood withdrawal via venous puncture in the elbow has a very low rate of adverse events. The needle puncture may cause bruising and in very rare cases an infection of the skin or blood vessel may occur at the puncture site.

A lumbar puncture is a minimal burdening to patients if the patient is in the right position and if the patient has a normal anatomy of the vertebrae. Usually, the lumbar puncture itself takes about 10 minutes and patients stay in the hospital afterwards for about half an hour. The most frequently occurring complication of lumbar puncture is post-lumbar puncture headache. This complication is much rarer when atraumatic spinal needles are used. If post-lumbar puncture headache occurs, subjects should take bed rest, drink ample water, and may use paracetamol if required. If the post-

lumbar puncture headache persists for more than a week, a blood patch may be considered which is usually effective in treating the headache.^{21, 22} Very rarely, infection such as meningitis or spinal abscess may occur. Patients will be contacted by phone three days after lumbar puncture to check whether the lumbar puncture has resulted in any persistent complaints. If there are complaints following the puncture, one of the neurologists will contact the patient to make sure adequate measures (e.g. a blood patch) are taken.

The potential risks related to lumbar puncture will be minimized in the following manner:

- Post-lumbar puncture headaches

We will use atraumatic spinal needles and will take out the needle with the stylet reinserted. To further reduce the risk, we will advise the patients to drink ample water and drinks with caffeine. A prospective study to investigate possible predictors for postdural puncture headache revealed young age and low BMI as significant risk factors.²³ Our study population will consist of middle-aged or older participants for the most part.

- Risk of infection

We will minimize the risk of infection by working under sterile conditions.

There is no benefit for the patients except for more general insight into the underlying pathophysiology of the hemorrhages related to their disease.

9.4 Compensation for injury

Subjects are insured by the insurance of the LUMC. The LUMC has a liability insurance which is in accordance with article 7, subsection 6 of the WMO. The insurance covers an amount of € 650.000 per participant, € 5.000.000 for the entire study, and € 7.500.000 per year for all studies from the same sponsor.

9.5 Incentives

All participants will be compensated for traveling costs.

10. ADMINISTRATIVE ASPECTS AND PUBLICATION

10.1 Handling and storage of data and documents

All study data will be handled confidentially. All data will be coded. The investigator will retain the originals of all source documents generated at LUMC for a period of 2 years after the report of the study has been finalized, after which all study-related documents will be archived for 15 years. The handling of personal data complies with the EU General Data Protection Regulation and the Dutch Act on Implementation of the General Data Protection Regulation (in Dutch: Uitvoeringswet AVG, UAVG). The person responsible for the processing of personal data will be [name] and [name].. Blood products and CSF for future biomarker research will be stored with coded medical information into the LUMC Biobank under 'Neurologische Ziekten'. Results of the Neuropsychological testing will be sent and stored in the digital CASTOR EDC database. CASTOR is

compliant with 21 CFR Part 11, ICH E6 GCP, GDPR, and HIPAA. ISO27001 and ISO9001 certified. Informed consents will be stored at the Neurology department of the LUMC at K5-106.

Participants may withdraw from this study at any time, without any consequences. This also accounts for the blood products and CSF, which will be destroyed after withdrawal. When measurements already have been performed, these data will still be used.

